6.9.9 Treatment-Emergent Adverse Events

All AEs that occur after the first administration of LR769 will be regarded as treatment emergent (TEAE). All AEs occurring from signing the Informed Consent up to the first administration of LR769 will also be collected and will be referred to as non-TEAEs. Adverse events that are present prior to the first administration of LR769 but subsequently worsen will be considered TEAEs.

A potential risk associated with the administration of LR769 is the occurrence of an allergic or anaphylactic type reaction to either the recombinant molecule or any of the potentially present host-related impurities. Specific emphasis will be put on the observation of the patient after initial administration of LR769 to detect the occurrence of any potential allergic reaction. Symptoms of such a reaction may consist of, but are not limited to:

- Skin redness, rash, hives

- Mucosal and/or skin swelling
- Difficulty breathing
- Hypotension
- Headache
- Dizziness
- Nausea

If any one or more of these symptoms occur, the responsible physician at the site will assess the patient and determine whether the symptoms are consistent with an acute allergic reaction and treat the symptoms accordingly.

Although reported to be rare in hemophilia patients, a potential risk associated with the administration of LR769 is an exaggerated PD action, leading to a thromboembolic event. Specific emphasis will be put on the observation of the patient directly after administration of LR769 as well as during the follow-up assessments to detect the occurrence of any thromboembolic events. Events that may occur are myocardial infarction, ischemic cerebrovascular accident, arterial thrombosis (eg, aorta, intestinal), DVT, and PE. In case signs and symptoms of any of these occur in the patients during the study, the responsible physician at the site will need to assess the symptoms and order and review diagnostic procedures (ECG, ultrasound, computed tomography [CT], magnetic resonance imaging [MRI], Doppler, D-dimer, etc) as appropriate to confirm or refute the diagnosis. In case of symptoms suggestive of a DVT or PE, the guidelines for diagnosis as published by the American College of Physicians ([Qaseem et al., 2007](#)) is suggested as guidance for determining the need for additional diagnostic tools.

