7.2 Surgery/Invasive Procedure and LR769 Treatment

7.2.1 Before Surgery/Invasive Procedure

- Confirm eligibility
- Physical examination (excluding height, including weight, which is the weight to be used for calculating dose of LR769) within 24 hours before the procedure
- An IV bolus dose of 75 µg/kg (for a minor surgery or other minor invasive procedure) or 200 µg/kg (for a major surgery or other major invasive procedure) of LR769 administered within ≤2 minutes before the surgical incision or start of the invasive procedure.
- Predicted surgery/invasive procedure characteristics
- Vital signs (blood pressure, heart rate, respiratory rate, and body temperature [sublingual or tympanic])
- Assessment of concomitant medications
- Assessment of AEs
- Immunogenicity sample (including storage serum sample for future use)

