9.3 Analysis Populations

The Efficacy Population is defined as all patients who receive LR769 treatment, undergo a surgical or invasive procedure, and have at least 1 efficacy assessment.

The Safety Population is defined as all patients who receive at least 1 dose of LR769.

All efficacy analyses will be performed on the Efficacy Population and all safety analyses will be performed on the Safety Population.

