9.6 Safety Endpoints and Analysis

Safety endpoints include the following:

- Analysis (including relationship to LR769, severity, and outcome) of AEs/SAEs between first LR769 administration and 28 (\pm 3) days after last administration of LR769
- Analysis of treatment-emergent thromboembolic events between start of procedure and 28 (\pm 3) days after last administration of LR769

- Analysis of allergic and anaphylactic reactions between start of procedure and 28 (± 3) days after last administration of LR769
- Analysis of treatment-emergent antibodies against LR769 or host-related impurities between start of procedure and 28 (± 3) days after last administration of LR769

All AEs will be coded using the Medical Dictionary of Regulatory Activities (MedDRA). The number and percentage of patients with any treatment-emergent AEs (TEAEs) and any treatment-emergent serious AEs (SAEs) will be presented for all patients. An AE will be considered treatment related if it has a definite, probable, or possible relationship to the study treatment or if the relationship to the study treatment is missing. AEs will be summarized at the patient level by MedDRA system organ class (SOC) and preferred term (PT) using frequencies and percentages. AEs will also be tabulated at the event level by SOC, PT, and severity and by SOC, PT, and relationship to study treatment.

The number and percentage of patients with any treatment-emergent thromboembolic event and/or allergic and anaphylactic reactions will be presented for all patients.

For vital signs and clinical laboratory test results (continuous parameters), descriptive statistics for the actual value at each timepoint and the change from baseline to each post baseline timepoint will be tabulated. Two-sided paired t-tests will be used to test whether the mean changes from baseline equal 0. Baseline is defined as the last measurement prior to study treatment. Descriptive statistics for immunogenicity data will also be produced for the specified timepoints.

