7.8.2 Adverse Events

All AEs will be coded using MedDRA (Version 15.0). An AE will be considered a treatment-emergent adverse event (TEAE) if it occurred or worsened after the first dose of study drug. In case a patient undergoes multiple procedures in the study, the TEAE will be assigned to the latest procedure prior to the event itself. Non-TEAEs are AEs occurring after signing Informed Consent but before the first administration of study drug. TEAEs will be summarized for the Safety Population. Non-TEAEs will be summarized for all enrolled patients.

The number and percentage of patients as well as the number of events will be summarized for any TEAEs, any treatment emergent SAEs, any treatment-related TEAEs, any non-treatment-related TEAEs, any TEAEs leading to discontinuation from the study, any TEAEs leading to study drug withdrawal and any TEAEs resulting in death. Summaries will be done stratifying by SOC and PT. An AE will be considered treatment related if it has a definite, probable, or possible relationship to the study treatment or if the relationship to the study treatment is missing. Additionally, a summary of TEAE's by SOC, PT, and severity grade will be created.

Separate summaries and listings will be provided for treatment-emergent thromboembolic events and allergic and anaphylactic reactions.

A data listing of TEAEs will be produced. Separate listings will also be prepared for SAEs, AEs leading to death, TEAEs leading to discontinuation from the study, TEAEs

leading to study drug withdrawal, thromboembolic AEs, and allergic and anaphylactic AEs. A listing of deaths will be provided as well, including information about the primary reason for death.

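### The allergic/anaphylactic, thromboembolic and antibody endpoints open at the start of the procedure, although the first LR769 dose precedes it (minor)

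*Protocol*

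**What the plan says.** Protocol 9.6 lists four safety endpoints. The general one covers "AEs/SAEs between first LR769 administration and 28" (±3) days after the last dose. The other three open later:

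- "Analysis of treatment-emergent thromboembolic events between start of procedure and 28" (±3) days after the last dose;
- "Analysis of allergic and anaphylactic reactions between start of procedure and 28" (±3) days after the last dose;
- "Analysis of treatment-emergent antibodies against LR769 or host-related impurities between start of procedure and 28" (±3) days after the last dose.

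The protocol synopsis and SAP section 5 carry the same four windows.

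On timing, protocol 7.2.1 places the initial bolus, 75 or 200 µg/kg depending on procedure type, among the activities before surgery: "of LR769 administered within ≤2 minutes before the surgical incision or start of the invasive procedure". On allergic reactions, protocol 6.9.9 states: "Specific emphasis will be put on the observation of the patient after initial administration of LR769". Protocol 9.3 does not require a procedure for safety analysis: "The Safety Population is defined as all patients who receive at least 1 dose of LR769".

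SAP 7.8.2 counts a TEAE from the first dose of study drug. For patients with more than one procedure it adds that "the TEAE will be assigned to the latest procedure prior to the event itself". SAP section 9, on departures from the protocol analysis, mentions only the dropped paired t-tests.

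**The concern.** Two start points are used for overlapping safety outcomes, and they are not the same moment. The interval between the initial bolus and the start of the procedure lies inside the AE/SAE endpoint but outside the endpoint named for allergic and anaphylactic reactions. That interval includes part of the observation period that protocol 6.9.9 singles out.

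The stake is a wrong count for a named risk in a very small trial. Under protocol 6.12 an acute allergic reaction associated with LR769 administration stops the study. A report could then describe a study stopped for such a reaction while the allergic-reaction endpoint, programmed to its literal window, shows none.

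The SAP 7.8.2 assignment rule raises a second question. Safety is analysed by procedure (SAP 7.1) and split by surgery type (SAP 7.8), and the initial dose differs by type. An event attached to the wrong procedure may therefore appear under the wrong type and initial dose.

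**Working it through.** The plan states no figure on this point, so there is nothing to reproduce. The check sets the time anchors side by side and then illustrates the size.

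**Anchors**

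| Item | Opens at | Source |
|---|---|---|
| AE/SAE endpoint | first LR769 dose | Protocol 9.6, SAP 5 |
| TEAE definition | first LR769 dose | Protocol 6.9.9, SAP 7.8.2 |
| Thromboembolic, allergic and antibody endpoints | start of procedure | Protocol 9.6, synopsis, SAP 5 |
| Initial bolus | before incision or start of procedure | Protocol 3.1, 7.2.1, Appendix 1 |

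**Uncovered interval** = start of procedure − first dose. Its length is unclear:

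- Protocol Tables 1 and 2 place the first dose within 2 minutes of the incision. If that describes a gap, the interval is at most about 2 minutes.
- Elsewhere the limit of 2 minutes or less reads as the duration of the bolus, and SAP Table 1 (major procedures) says only that the dose comes before the incision. On that reading no limit is stated.
- If a reaction prevents the procedure from starting, the window never opens, yet the patient is in the Safety Population.

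**Effect by endpoint**

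- Allergic/anaphylactic: affected when onset falls in the interval or the procedure is cancelled. A first-dose reaction with onset after the procedure starts is inside the window.
- Thromboembolic: small if the interval is about 2 minutes.
- Antibodies: negligible. The pre-procedure sample is the baseline. The later samples (7–14 days after the first dose, then 48 hours and 28 days after the last) fall inside the window once a procedure has started.

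**Illustration at the minimum size** (6 patients and 12 procedures, protocol 3.3). Take one reaction in the interval before a procedure that then goes ahead.

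- Per patient, counted from first dose: 1/6 = 16.7%. Counted from start of procedure: 0/6 = 0%.
- Per procedure: 1/12 = 8.3% against 0/12 = 0%.

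These differences arise only if the literal window is programmed.

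**Assignment rule.** Suppose a patient has a minor procedure and later re-enters for a major one, and reacts to the 200 µg/kg bolus before the second incision. If procedure means the operation, the latest one before the event is the minor one. Assuming 6 major and 12 − 6 = 6 minor procedures, the major stratum shows 0/6 instead of 1/6 (16.7%), and the minor stratum shows 1/6 instead of 0/6. The overall count stays at 1/12. A reaction before such a patient's first operation has no prior procedure to be assigned to.

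**The case against.** The strongest reply is that the planned outputs already count from dosing. Protocol 9.6 goes on to present patients with treatment-emergent thromboembolic events and allergic reactions. SAP 7.8.2 plans separate summaries and listings of these events with no filter on procedure start. The three bullets are then endpoint titles, and 7.8.2 describes how the tables are built.

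This stands as far as the consequence goes. A reader might infer that such reactions are lost to the trial, and the documents do not support that. The event enters the AE/SAE endpoint and the TEAE tables. Under protocol 6.9.9 it is reported on the SAE timeline even if not serious, and the stopping rule in 6.12 is tied to administration. A reader might also infer that any reaction to the first dose is excluded, or that all three endpoints suffer equally. The working shows neither is so.

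The reply does not remove the inconsistency. The thromboembolic bullet says treatment-emergent and still adds the later start, so the start reads as a further restriction. The allergic bullet omits treatment-emergent altogether. In the summary sentences it is unclear whether that adjective reaches allergic reactions. A programmer could follow either rule, and SAP section 9 does not choose.

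On the assignment rule, SAP 7.1 uses procedure for a study entry as well as for an operation. On that sense, a reaction to the second entry's bolus belongs to the second procedure. Misassignment is therefore possible, not certain. That sense does not rescue the endpoint windows, because protocol 7.2.1 explicitly places the bolus before the invasive procedure starts.

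**Conclusion.** The inconsistency is real and minor. As written, the three endpoint windows disagree with the AE/SAE endpoint, the TEAE definition and the planned treatment-emergent summaries. The practical consequence is confined mainly to allergic/anaphylactic reactions that begin before the procedure starts or prevent it from starting.

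The illustrated change from 16.7% to 0% per patient, or from 8.3% to 0% per procedure, rests on three assumptions: the minimum trial size, one such event, and an analyst who applies the literal window. It is not a prediction of what the tables will show. The stratum error rests on reading procedure as the operation, and it moves an event between surgery types without changing the overall count.

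A reader might conclude that this undermines the trial's safety conclusions. It does not, because the events remain visible in the other safety outputs. The primary efficacy analysis is untouched.

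**What to change.** In the protocol synopsis, protocol 9.6 and SAP section 5, open the thromboembolic, allergic/anaphylactic and antibody windows at the first LR769 administration of the treatment course concerned, matching the AE/SAE endpoint. In SAP 7.8.2, assign each TEAE to the latest treatment course, defined by its first LR769 dose, and include courses whose procedure never started.

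The timing of the initial dose relative to the incision is worded differently in protocol Table 1 and SAP Table 1, and those passages should be reconciled. The proposed anchor works whichever wording is kept.

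The cost is a few words in each document, with no change to treatment or visits. Protocol 6.9.1 already records AE start date and time, and protocol 5.7 has home dose times entered in the diary. Capture of in-hospital dose times in the eCRF should be confirmed. The only downside is that the reported rate for the named endpoints may be slightly higher.

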9.7 Interim Analysis

There are no planned interim analyses for this study.

10 ADMINISTRATIVE CONSIDERATIONS

10.1 Investigators and Study Administrative Structure

The Sponsor will contract a CRO to perform specific study related tasks. The division of responsibilities will be documented in mutually agreed documents. Written procedures will be used in order to assure that the study is conducted according to all applicable rules and regulations.

The investigators will ensure that this study is conducted in accordance with the ethical principles that have their origin in the Declaration of Helsinki and that are consistent with Good Clinical Practice (GCP) and any other local regulations and guidelines.

The investigators will review all study-related documents including the protocol and the current version of the [Investigator's Brochure](#). It is obligatory that the Principal Investigator be familiar with the protocol and all sections of the [Investigator's Brochure](#) prior to initiation of the study.

10.2 Institutional Review Board (IRB) or Independent Ethics Committee (IEC) Approval

A copy of the protocol, [Investigator's Brochure](#), proposed Informed Consent/Assent Form and any other written patient information must be submitted to the IRB/IEC for written approval. A copy of the written IRB/IEC approval of the protocol and Informed Consent/Assent form must be received by the Sponsor before recruitment of patients into the study and shipment of investigational drug.

The Principal Investigator/CRO must submit and, where necessary, obtain approval from the IRB/IEC for all subsequent protocol amendments and changes to the Informed Consent/Assent form. The Principal Investigator/CRO will notify the IRB/IEC of deviations from the protocol or SAEs/reportable safety events at the site or reports of such events received from the Sponsor in accordance with local procedures.

The Principal Investigator/CRO will be responsible for obtaining annual IRB/IEC approval and renewal throughout the duration of the study.

The Principal Investigator will promptly report to the IRB/IEC all changes in research activity and all unanticipated problems involving risks to human patients and will not make any changes in the research without prior Sponsor and IRB/IEC approval, except where necessary to eliminate immediate hazards to human patients

10.3 Ethical Conduct of the Study

This study will be conducted in compliance with GCP as described in the International Conference on Harmonisation (ICH) document "Guidance for Industry-E6 GCP: Consolidated Guidance" dated April 1996. These practices are consistent with the principles

stated in the Declaration of Helsinki (October 2013 revised version). All other applicable regulations will be adhered to.

10.4 Patient Information and Consent

Written Informed Consent must be obtained for all patients who are potential study candidates before any study-specific tests or procedures are performed. Patients or the parent(s)/legal guardian(s) of the patients who meet general entry criteria will be asked to sign the study specific, IRB/IEC approved Informed Consent Form before any study-specific test or procedures are performed. The written Informed Consent will be obtained after the context of the study has been fully explained to the patient or patient's parent(s)/legal guardian(s) in a language that is easily understood by the patient or the parent(s)/legal guardian(s). There must also be adequate opportunity to ask questions and have those questions answered to their satisfaction. Study personnel will explain that even if a patient agrees or the parent(s)/legal guardian(s) agrees to allow a child to participate in the study and signs an Informed Consent Form, the study-specific test or procedures may demonstrate that the patient is not a candidate for the study.

The written Informed Consent will be prepared in the language(s) of the potential study population and will be administered according to national requirements.

The patient may, depending on his age, receive age-appropriate information as well as be asked to sign and date an Assent Form. Age of providing information and Assent Form may differ between institutions and will be determined by local law and IRB or IEC requirements.

10.5 Patient Confidentiality

Patient participation is voluntary and patients or a patient's parent(s)/ legal guardian(s) may refuse to participate or withdraw from the study at any time and for any reason. Patients and/or their parent(s)/legal guardian(s) will be informed that information about them/their child is being entered into a study database and their consent will be obtained and recorded. Patients will be identified only by a patient number and date of birth. They will be informed as to the strict confidentiality of their patient data, and that their medical records may be reviewed for study purposes by authorized individuals other than their treating physician.

10.6 Study Monitoring

Monitoring visits to the study sites will be conducted periodically during the study according the study monitoring plan to ensure that all aspects of the current, approved protocol are being followed. Monitors will be given direct access to original source documents which will be reviewed for verification of 100% of data captured in the eCRF. For this study, source documents include but are not limited to the Informed Consent/Assent Form, patient's medical records, patient diaries, laboratory results, reports of SAE's, and drug accountability logs. It is important that the investigator and relevant study personnel are available during monitoring visits and audits and that sufficient time is devoted to the process.

10.7 Case Report Forms and Study Records

Patient data will be collected both electronically and on paper. The investigators must ensure the accuracy and completeness of the recorded data and provide a signature on the appropriate eCRFs. The investigator's signature for specific eCRFs will be documented in compliance with ICH/GCP guidelines. Visual and/or computer data review will be performed to identify possible data discrepancies. Data cleaning will be performed on all data in the eCRF. Queries will be created in the data management system and will be issued for appropriate response

10.8 Data Monitoring Committee

The Data Monitoring Committee (DMC) is responsible for the oversight of patient safety. The DMC will consist of 3 specialists in the care of hemophilia patients. DMC members will be independent of the study and Sponsor. During the course of the trial, the DMC will review immediate serious adverse drug reactions and quarterly review of SAE listings. In addition the DMC will review the data and recommendation from the DMC in the [PERSEPT 2](#) pediatric study to determine whether enrollment of patients <12 years of age is appropriate for this study.

The DMC will make recommendations, as appropriate, for study modification or termination because of concerns over patient safety or issues relating to data monitoring or quality control. This will be submitted in writing to the sponsor's Medical Monitor for consideration and final decision. However, if the DMC at any time determines that a potential serious risk exists to patients in the study, the DMC Chairperson will immediately notify the Sponsor's Medical Monitor per the DMC Charter.

10.9 Protocol Deviations

Deviations from clinical protocol requirements will be reviewed and evaluated on an ongoing basis and, as necessary, appropriate corrective actions put into place.

An important subset of protocol deviations is "important protocol deviations," which are defined by ICH E3 as "protocol deviations that may significantly impact the completeness, accuracy, and/or reliability of the study data or that may significantly affect a patient's rights, safety, or well-being. For example, *important protocol deviations* may include enrolling patients in deviation of key eligibility criteria designed to ensure a specific patient population or failing to collect data necessary to interpret primary endpoints, as this may compromise the scientific value of the trial." An example of an important protocol deviation provided in the guideline is "deviations related to entry criteria, conduct of the trial, patient management, or assessment." An analysis of important protocol deviations will be presented in the CSR.

